1. INTRODUZIONE

1.1 Background

Viral, bacterial, and protozoal infections are associated with a diverse clinical spectrum of symptoms, including fatigue, difficulty concentrating, depression, sleep disturbances, gastrointestinal disorders, and musculoskeletal pain [1-3]. In previous coronavirus epidemics such as Severe Acute Respiratory Syndrome (SARS) and Middle East Respiratory Syndrome (MERS), studies have linked the infection to the possible development of Chronic Fatigue Syndrome/Myalgic Encephalomyelitis (CFS/ME) [4-6]. In particular, a study by Lam et al. conducted on 233 SARS survivors revealed that after 4 years, 27.1% of patients met the criteria for a CFS/ME diagnosis [7]. In the field of gastroenterology, several studies have demonstrated that previous infections of the gastrointestinal tract can lead to Irritable Bowel Syndrome (IBS) and CFS/ME. A study conducted on a Norwegian population of 576 individuals followed for 10 years after a Giardia Lamblia epidemic showed that the relative risk of developing IBS was 4.74 compared to an uninfected control group, while the relative risk of CFS/ME was 3.01 [8]. Another significant German study involving a large number of patients (508,278) found an increased relative risk of IBS and CFS/ME (1.73 and 2.08, respectively) in patients diagnosed with infectious gastroenteritis [9]. Several mechanisms may be involved in the pathogenesis of CFS and IBS associated with previous infection. Among these, it is possible that viral, bacterial, or protozoal infections lead to a modification of the intestinal microbiota in qualitative and quantitative terms. This alteration could result in a pro-inflammatory phenotype, leading to the release of bacterial toxins and inflammatory cytokines into the systemic circulation through areas of altered intestinal permeability (leaky gut) [10-17]. The same alteration of intestinal permeability and the microbiota may also be involved in various neurological and psychiatric disorders reflecting an alteration of the so-called "brain-gut axis" [11,18-20]. Additionally, cognitive impairment may play a role in the perception of fatigue. Persistent cognitive impairments have been documented following SARS-CoV-2 infection [21-23],

and a recent Italian study on a group of 38 hospitalized COVID-19 patients demonstrated deficits in processing speed and verbal memory [23]. Several studies have attempted to intervene in the dysbiotic intestinal pathogenic mechanism of CFS/ME. A systematic review with meta-analysis from 2018 analyzed the use of probiotics in the context of CFS/ME and IBS in 25 studies. The possible therapeutic role of probiotics is recognized, but the low quality of the trials, overall lack of evidence, and the different composition of these products do not allow for the affirmation of their actual effectiveness [24]. Similar conclusions are reported in recent American guidelines on IBS, which confirm the role of infections and the microbiota in the pathogenesis of this disease but also lament the poor quality of evidence (mostly based on monocentric studies with small sample sizes) to recommend their systematic use [25]. The same guidelines cite a meta-analysis by Ford et al. from 2014, which summarizes the results of 37 randomized clinical trials in IBS and concludes that probiotics have been associated with improvements in overall symptomatology, abdominal pain, bloating sensation, and flatulence [26]. However, the authors themselves declare that the evidence of probiotic effects is influenced by the different composition of commercially available products and the poor quality of the conducted studies [26].

During the current COVID-19 epidemic, a series of scientific studies have demonstrated an alteration in the composition of the intestinal microbiota during SARS-CoV-2 infection [27-29]. This alteration, compared to the gut flora of healthy controls, appears to persist beyond the hospitalization period, be independent of the administered therapy, be associated with the presence of inflammatory taxa, and be more extensive and radical than that induced by H1N1 influenza infection [27-29].

Furthermore, starting from the first wave of COVID-19, a new post-infectious syndrome called "Long-Covid19 Syndrome" has been described in several countries, characterized by the persistence of clinical symptoms after recovery from COVID-19 according to WHO criteria [30,31]. Carfi et al. analyzed 143 hospitalized patients who were discharged after an average of 60 days from the onset of the disease and found that up to 87.4% of patients had at least one persistent

symptom, with fatigue being the main one (53.1%) [32]. In a study conducted using an online platform, Goërtz et al. demonstrated that in a cohort of 2113 patients (including patients with a confirmed or suspected diagnosis of COVID-19), the number of symptoms experienced 79 days from the onset of the illness had significantly reduced, but at the same time, only 0.7% of patients were symptom-free. Once again, fatigue was the most reported symptom (87%) [33]. A study by Townsend et al. from Ireland, involving 128 patients, approximately half of whom were hospitalized for COVID-19, evaluated after a median time of 72 days, showed that only 42% of these patients had a health status comparable to that before the infection. 52% of the subjects met the diagnostic criteria for fatigue, with Chalder Fatigue Scale (ChFS) scores similar to those of patients with CFS/ME. Surprisingly, the state of fatigue does not seem to be correlated with the clinical severity of SARS-CoV-2 infection or the presence of inflammatory changes (e.g., white blood cell count, neutrophil count, neutrophil-to-lymphocyte ratio, and levels of PCR, LDH, IL-6), suggesting a more subtle etiopathogenic mechanism in line with other observations in CFS/ME [34]. Another Norwegian study observed the prevalence of fatigue in a cohort of non-hospitalized SARS-CoV-2 positive patients, using the ChFS via postal survey conducted at a distance from the diagnosis of COVID-19. The 458 enrolled patients responded after a median time of 117 days from SARS-CoV-2 infection, and 46% showed a ChFS score (in dichotomous mode) compatible with clinically significant fatigue, while the Likert Scale score of the same scale differed significantly from that obtained from a cohort of healthy subjects [35]. Finally, in our own case series of 164 patients studied five months after SARS-CoV-2 infection, compared to a control group of 183 subjects, the relative risk of CFS was increased by 2.24.

VSL#3® is a patented high-concentration blend (450 billion bacterial units) of live and lyophilized lactic acid bacteria and bifidobacteria, belonging to eight different strains (one strain of *Streptococcus thermophilus* BT01; three strains of *Bifidobacteria*: *B. breve* BB02, *B. animalis* subsp. *lactis* BL03 (formerly known as *B. longum* BL03), and *B. animalis* subsp. *lactis* BI04 (formerly known as *B. infantis* BI04); four strains of *Lactobacilli*: *L. acidophilus* BA05, *L.*

plantarum BP06, L. paracasei BP07, and L. helveticus BD08 (formerly identified as L. delbrueckii subsp. bulgaricus BD08)).

Animal studies support the biological plausibility that modulation of the microbiome can affect perception and cognitive-behavioral mechanisms [36]. In an exploratory study in patients with IBS, *Bifidobacterium Longum* reduced depression scores and improved the patients' quality of life. These improvements were associated with changes in brain activation patterns indicating that the probiotic reduces limbic reactivity [37]. Recently, a comparative study of VSL#3 versus a LOW-FODMAP diet was published, showing that both treatments had fundamentally the same efficacy [38].

2. STUDY OBJECTIVE/HYPOTHESIS

2.1 Primary Objectives

The primary objective of this study is to test whether a high-concentration probiotic formulation (e.g., VSL#3®) can reduce the degree of clinically significant fatigue in ambulatory patients suffering from Long-Covid-19 Syndrome, i.e., the persistence of systemic symptoms 4 weeks after molecular detection of SARS-CoV-2

2.2 Secondary Objective(s)

1. To determine if this high-concentration probiotic formulation can improve scores of anxiety, depression, quality of life, gastrointestinal symptoms, cognitive deficits, performance, psychological distress, and clinical evaluation of the study patients.
2. To assess the immunological profile of inflammation markers in blood and bacterial species in feces in patients treated with VSL#3® compared to patients treated with a placebo. Any differences before and after treatment will be identified.

3. STUDY DESIGN

3.1 Study Design

Our study is a double-blind, randomized, placebo-controlled trial. Anticipating a higher representation of female subjects in our sample, we hypothesized a stratified block randomization by sex. This is a single-center study conducted in an outpatient setting, and currently hospitalized patients will not be recruited.

3.2 Inclusion Criteria

Patients who meet all of the following criteria will be included:

- Ambulatory patients who have signed informed consent.
- Age above 18 years and below 65 years.
- Previous diagnosis of SARS-CoV-2 infection, documented by molecular nasopharyngeal or antigen swab.
- Not currently undergoing isolation or quarantine.
- Not having used antibiotic products within the 30 days preceding the trial.
- Chalder Fatigue Scale (in dichotomous form) ≥ 4 , possibly associated with signs and symptoms of Long-Covid-19 Syndrome [31,32]: signs and symptoms that develop during or after SARS-CoV-2 infection, persist for more than 4 weeks, and are not reasonably explained otherwise; signs and symptoms include fatigue, sleep disturbances, cognitive deficits (i.e., brain fogging, loss of concentration and memory, anxiety, depression), muscle weakness, joint pain, gastrointestinal alterations (reduced appetite, nausea, changes in bowel habits such as constipation and/or diarrhea, abdominal pain)

3.3 Exclusion Criteria

Patients with at least one of the following criteria will be excluded:

- Moderate to severe cardiovascular and pulmonary diseases with organ dysfunction (NYHA >2 , Borg scale ≥ 2).
- Decompensated endocrine and metabolic diseases (Child-Pugh cirrhosis $\geq B$, decompensated hypo/hyperthyroidism, decompensated adrenal insufficiency).
- Pre-existing diagnosis of FM, CFS/ME, and/or IBS prior to SARS-CoV-2 infection.

- Confirmed diagnoses of neurological disorders, psychiatric illnesses, and cognitive impairments prior to SARS-CoV-2 infection.
- Previously confirmed diagnoses of chronic musculoskeletal disorders prior to SARS-CoV-2 infection.
- Refusal to participate in the study / refusal to allow the processing of personal data.
- Pregnancy or breastfeeding.
- Alcohol or drug dependency in the previous years.
- Use of other probiotics during the trial.
- Use of antibiotics during the trial and in the 30 days preceding it.
- Substantial change in diet during the trial.
- Participation in another clinical study in the 30 days preceding or previous participation in the same trial.
- Known intolerance/hypersensitivity to the investigational product or the excipients of the placebo formulation.

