4. PROCEDURES RELATED TO THE STUDY

4.1 Intervention Patients

Patients will be referred by the Pneumology and Infectious Diseases outpatient clinics for a preliminary evaluation of inclusion and exclusion criteria, within the context of scheduled visits for sequelae of SARS-CoV-2 infection. The recruitment phase is divided into an initial screening visit (Visit 1, t-2) to determine if the patient meets the inclusion/exclusion criteria. Following this visit, a

14-day run-in period will be conducted to screen for non-adherent patients, i.e., those who do not show up for the subsequent visit. The patient will return for a visit at 14 days (Visit 2, t0) when randomization will occur, and the patient will be assigned to the treatment or placebo group. The patient will be instructed to take the treatment (supplement or placebo) at the prescribed dosage of two sachets per day for a consecutive and continuous period of four weeks. During this visit, all immunological and microbiological analyses will be performed, including the collection of 20 mL of blood and 1 g of fecal material. The patient will also complete clinical questionnaires to assess the primary and secondary endpoints. The clinical questionnaires will be stored in a deidentified form at the Gastroenterology and Endoscopy Unit, while the biological samples will be shipped and analyzed at the Mucosal Immunology Laboratory of the IEO. Considering the short duration of the study and the lack of literature data demonstrating a clear benefit of VSL#3 on this syndrome, no crossover between study arms is planned under any circumstances. During the study, the use of immunosuppressants or immunomodulators, glucocorticoids, opioids, antidepressants, or anxiolytics at regular and continuous dosages is not allowed. If there is a clinical necessity for antibiotic therapy, it will result in discontinuation of the study. After completing the 28-day treatment period, the patient will return for a visit (Visit 3, t4) where immunological and microbiological analyses will be repeated, and questionnaires will be completed again to evaluate the primary and secondary endpoints. An additional visit with completion of clinical questionnaires will be scheduled 28 days after the end of the treatment (Visit 4, t8) to assess whether any response is maintained at the end of the treatment period.

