6. STUDY DURATION / TIMELINE

The study will have a total duration of 70 days per enrolled patient. Please refer to the attached Gantt chart.

Study Start: 09/2022 Recruitment Closure: 12/2022 Study End: 07/2023

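### Section 3.3 bars probiotics only during the trial, with no look-back like the 30 days set for antibiotics, so the t0 stool and serum of recent users may not be an unexposed baseline

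*Combined protocol and SAP*

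**What the plan says.** Section 3.3 lists two neighbouring exclusions that differ in reach. For probiotics it is "Use of other probiotics during the trial". For antibiotics it is "Use of antibiotics during the trial and in the 30 days preceding it". Section 3.2 repeats the antibiotic look-back as an inclusion criterion: "Not having used antibiotic products within the 30 days preceding the trial". It has no matching item for probiotics.

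The only other rule that looks back at recent exposure to a study product is "Participation in another clinical study in the 30 days preceding or previous participation in the same trial". It does not reach someone who used a commercial product on their own initiative.

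Section 4.1 places a run-in between Visit 1 and randomisation at Visit 2 (t0), with one stated purpose: a "14-day run-in period will be conducted to screen for non-adherent patients, i.e., those who do not show up for the subsequent visit". Blood and stool are first taken at Visit 2: "During this visit, all immunological and microbiological analyses will be performed". Section 6 adds: "The study will have a total duration of 70 days per enrolled patient".

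No section sets a probiotic washout, and none asks for earlier probiotic use to be recorded. The data items named in Section 10.1 are demographics, infection history, questionnaire results and laboratory data.

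**The concern.** The antibiotic rule shows that the authors wanted a recent exposure that alters the microbiota cleared before entry. The exposure closest to the intervention has no such rule. The word used for the excluded products also leaves it unclear whether earlier use of VSL#3 itself counts.

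What is most clearly at stake is the baseline. Secondary objective 2 (Section 2.2) looks for differences before and after treatment in inflammation markers and faecal bacteria. The last endpoint in Section 5.2 takes alpha and beta diversity and correlates them with the fatigue response. Both rest on the t0 samples. In a patient who took a probiotic until shortly before t0, that sample may not show an unexposed state, and part of the change from t0 to t4 may reflect the end of the earlier product. This ground needs no assumption about how such patients respond.

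A second, weaker ground is the primary endpoint. If the study product adds less in people who recently used a similar one, the difference between arms in Chalder score shrinks.

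**Working it through.** **1. Timeline.** Run-in 14 days, treatment 28 days and follow-up to Visit 4 of 28 days (Section 4.1): 14 + 28 + 28 = 70. This equals the duration in Section 6, so the protocol counts the run-in as part of the study.

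**2. Days barred before the t0 samples, by where the trial starts.**

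| Exposure | Trial starts at Visit 1 | Trial starts at Visit 2 (t0) |
|---|---|---|
| Antibiotics | 30 + 14 = 44 | 30 |
| Other probiotics | 0 + 14 = 14 | 0 |
| Earlier self-directed VSL#3 | not clearly covered | not clearly covered |

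The 70-day count favours the middle column, but the start of the trial is nowhere defined. On either reading the probiotic window is 30 days shorter than the antibiotic one.

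**3. The plan's sample size.** This point does not contest the figure in Section 7.1; it is reproduced only as a base for step 4. Inputs: 30% and 60%, two-sided 0.05, power 80%. Read as responder proportions in a pooled two-proportion test, with mean proportion 0.45:

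n = [1.960 × √(2 × 0.45 × 0.55) + 0.842 × √(0.30 × 0.70 + 0.60 × 0.40)]² / 0.30² ≈ 42 per arm, power 0.800.

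This matches the stated 42. The match depends on reading the percentages as proportions, since no standard deviation is given for a comparison of means.

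**4. Possible dilution (illustration only).** The documents do not give the share f of recent users. Assume that they gain nothing over placebo. The probiotic rate becomes 0.30 + 0.30 × (1 − f).

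| f (assumed) | Probiotic rate | Power at 42 per arm | Patients per arm for 80% |
|---|---|---|---|
| 0 | 0.600 | 0.80 | 42 |
| 5% | 0.585 | 0.76 | 47 |
| 10% | 0.570 | 0.71 | 52 |
| 20% | 0.540 | 0.61 | 66 |
| 30% | 0.510 | 0.50 | 85 |

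A comparison of means sized for 80% power at 42 per arm gives nearly the same powers. The table shows that the design has little margin if dilution occurs. It does not show that dilution occurs. The assumption is severe, because it gives every prior user zero benefit whatever product they took and for how long.

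**The case against.** The other side has a good case, and much of it stands.

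- **The run-in gives some clearance.** On the 70-day count, other probiotics are already barred for 14 days before t0. This is the better reading, so nobody should conclude that there is no clearance at all. But the run-in is described only as an adherence screen, no instruction to stop probiotics is attached to it, and the documents cannot settle whether 14 days is enough.
- **Randomisation protects the comparison.** Allocation is 1:1 and any earlier product is stopped in both arms, so prior use balances in expectation. A reader might infer bias between arms; the documents do not support that. Noise, possible dilution and chance imbalance remain, since sex is the only stratification factor.
- **The direction is open.** Less benefit in prior users would narrow the arm difference. If an earlier product had been helping, its withdrawal could worsen placebo patients and widen it.
- **Visit 4 proves little.** It is tempting to say that the plan itself assumes an effect lasting 28 days, because of "Visit 4, t8) to assess whether any response is maintained at the end of the treatment period". That visit is described as a questionnaire visit and asks an open question about symptoms. It says nothing about how long stool or serum carry-over lasts.
- **Antibiotics and probiotics need not share a window.** True: the difference is not a contradiction. But no reason is given for it, and this is the exposure nearest to the one under test.
- **Few patients may be affected.** Pre-existing IBS is excluded, which may remove some regular users. The number left is unknown and, as planned, will stay unknown because prior use is not recorded.

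**Conclusion.** The gap is real. As written, Section 3.3 lets a recent probiotic user enter with at most 14 days barred before t0 (none if the trial starts at t0), and leaves earlier VSL#3 use unclear. The firm consequence is that some t0 samples may not be an unexposed baseline, which adds noise to secondary objective 2 and to the microbiota endpoint and its correlation with fatigue response.

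For the primary endpoint, dilution is possible but cannot be sized. A reader might go further and call these patients likely non-responders, or assert a definite loss of power. Neither follows: the documents contain no data on the number of prior users or on their response, and the shares of 5% to 30% used above are assumptions.

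No figure in the plan is wrong on this account. The point is a cheap improvement of minor to moderate weight.

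**What to change.** 1. Reword the exclusion in Section 3.3 so that it covers any probiotic, including the study product outside its assigned use, both during the trial and in the 30 days before it. The 30 days are borrowed from the antibiotic rule and not shown to be the best length for probiotics; the investigators may set and justify another.
2. Define the start of the trial once, at Visit 1 or at Visit 2, and apply it to the antibiotic and probiotic criteria alike. With a 30-day look-back both windows before t0 are then equal: 44 days if the start is Visit 1, 30 if it is t0.
3. Record prior probiotic use at Visit 1 (product and date last taken), and plan a sensitivity analysis of the microbiota, cytokine and fatigue results by prior use.

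The cost is one line in the protocol, one screening question, and a few patients deferred or excluded. Deferral matters somewhat, because this is a single centre with recruitment planned from 09/2022 to 12/2022. The gain is hard to obtain later: an exposed t0 sample cannot be retaken, and without a record of prior use no sensitivity analysis is possible.

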3.4 Study Withdrawal Criteria

- Onset of hypersensitivity to the study product or the placebo
- Clinical necessity for the use of antibiotics, immunosuppressants or immunomodulators, glucocorticoids, opioids, antidepressants, or anxiolytics at regular and continuous dosages.

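### Withdrawal for needing another drug, with t4 scheduled only after completed treatment, leaves some randomised patients without a primary endpoint and outside the intention-to-treat analysis

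*Combined protocol and SAP*

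**What the plan says.** All references are to the combined protocol and SAP.

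- **3.4 Study Withdrawal Criteria.** Besides hypersensitivity, the ground for withdrawal is "Clinical necessity for the use of antibiotics, immunosuppressants or immunomodulators, glucocorticoids, opioids, antidepressants, or anxiolytics at regular and continuous dosages".
- **4.1 Intervention Patients.** The ban is restated for every class except antibiotics: "During the study, the use of immunosuppressants or immunomodulators, glucocorticoids, opioids, antidepressants, or anxiolytics at regular and continuous dosages is not allowed". For antibiotics, 4.1 says that clinical need leads to discontinuation of the study.
- **4.1, visit schedule.** "After completing the 28-day treatment period, the patient will return for a visit (Visit 3, t4"; the questionnaires are then completed again. A further visit, t8, follows 28 days after treatment ends.
- **5.1.** The primary endpoint compares the arms on the Chalder Fatigue Scale at t4.
- **7.2.** Intention-to-treat and per-protocol analyses are both planned. The section does not define the intention-to-treat set or say how a missing t4 score is handled.
- **3.2 and 3.3, entry criteria.** Antibiotics are covered ("Not having used antibiotic products within the 30 days preceding the trial" and "Use of antibiotics during the trial and in the 30 days preceding it"). The other five classes in 3.4 are not named.

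**The concern.** An intention-to-treat comparison keeps the protection of randomisation only if randomised patients are followed to the endpoint whatever happens to their treatment. Here the plan appears to join two things that should be separate: stopping the study product and leaving follow-up.

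The triggering events are not neutral. Section 3.2 counts anxiety and depression among the syndrome's symptoms, so a patient who is doing badly in the four weeks after randomisation is a plausible candidate for a new antidepressant or anxiolytic. Similar reasoning could apply to opioids or glucocorticoids for persisting pain. If such patients vanish before t4, the patients who remain are a selected group. If the selection differs between arms, for example because one arm is doing worse, the comparison is distorted. At stake are the completeness of the primary analysis and its claim to be intention-to-treat.

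**Working it through.** **1. Following one patient through the text.** A patient is randomised at Visit 2 (t0). In week 2 regular use of an antidepressant becomes clinically necessary. Under 3.4 the patient meets a withdrawal criterion; under 4.1 continued use is barred. The only description of the t4 visit places it after the 28 days of treatment have been completed, which this patient will not do. No other section schedules a t4 questionnaire. The patient was randomised but has no primary endpoint.

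**2. The window.** Only withdrawals between t0 and t4, 28 days, affect the primary endpoint. A withdrawal in the following 28 days affects t8 only, which is secondary.

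**3. The plan's own figures.** The 42 per arm in 7.1 reproduces as a comparison of 30% with 60%, two-sided 0.05, power 80%:

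n = [1.960·√(2 × 0.45 × 0.55) + 0.842·√(0.30 × 0.70 + 0.60 × 0.40)]² / 0.30² = (1.379 + 0.565)² / 0.09 ≈ 42.

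The recruitment target is 48 per arm, which leaves 48 − 42 = 6 per arm for losses. Inflating for 15% gives 42 / 0.85 = 49.4, so 50, or 42 × 1.15 = 48.3, so 49; the stated 48 is within 2 of either. The present point does not depend on this small difference. The allowance replaces numbers; it does not make the remaining patients representative of those randomised.

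**4. How a loss carries through.** In one arm, let m be the share without a t4 score and δ the mean score of the lost patients minus that of the observed patients (higher means more fatigue). Then

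mean of all randomised = observed mean + m·δ.

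The observed placebo-minus-probiotic difference is therefore too small by m_P·δ_P − m_T·δ_T, where P is placebo and T is probiotic. If the m and δ are the same in both arms, this is zero. The shift in one arm's mean, per point of δ, for assumed values of m:

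| m | shift per 1 point of δ (0–33 scale) |
|---|---|
| 0.05 | 0.05 |
| 0.10 | 0.10 |
| 0.15 | 0.15 |

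The last row uses the plan's full dropout rate, which covers all reasons, so it is a generous share for this rule alone. The documents give neither m for this rule nor δ, so no error in the treatment effect can be computed.

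**5. Entry side.** Section 3.4 names six classes; one (antibiotics) has an entry criterion and five do not. The nearest exclusions, "Confirmed diagnoses of neurological disorders, psychiatric illnesses, and cognitive impairments prior to SARS-CoV-2 infection" and "Previously confirmed diagnoses of chronic musculoskeletal disorders prior to SARS-CoV-2 infection", stop at diagnoses made before the infection. They do not reach a drug started afterwards. The run-in is described only as a test of attendance: "14-day run-in period will be conducted to screen for non-adherent patients, i.e., those who do not show up for the subsequent visit". Against that, section 6 gives 70 days per patient, and 14 + 28 + 28 = 70, whereas 28 + 28 = 56. The run-in therefore appears to lie inside the study, and the 4.1 ban can be read as applying before randomisation.

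**The case against.** **Nothing forbids a t4 score after withdrawal.** This is true. The protocol is silent, and a site could take intention-to-treat in 7.2 as an instruction to keep following such patients. But the heading of 3.4, the antibiotic sentence in 4.1 and the wording of the t4 visit all point the other way, and no procedure tells staff to obtain the score.

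**The trial is double-blind and short, and 15% dropout is allowed for.** Blinding makes it unlikely that knowledge of treatment drives the decision to prescribe. It does not stop a patient's actual state from driving it, and that state may depend on the arm. The short window limits the number of events, but the number is not known. The allowance addresses precision only.

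**A score taken after starting another drug is contaminated.** In part this stands: such a score reflects both treatments. Intention-to-treat nevertheless asks for the outcome under assignment, and the per-protocol analysis already planned can set these patients aside.

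**A stronger reading about entry.** A reader might infer from 3.2 and 3.3 that the handling of patients already on one of the five classes is wholly open, and that the trial loses power or is biased as a result. The documents do not support that. Section 4.1 states a plain prohibition, and the 70-day duration places the run-in within it, so the text already points to not randomising a current user. Use present at entry also predates randomisation, so losses from it would be expected to balance across arms. No share of users is given from which a loss of power could be worked out.

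**Conclusion.** The point holds as a follow-up problem. As written, withdrawal under 3.4 before t4, combined with a t4 visit tied to completed treatment, removes randomised patients from the primary endpoint for post-randomisation reasons that may relate to outcome. The intention-to-treat analysis in 7.2 would then be incomplete.

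This rests on reading withdrawal in 3.4 as leaving the study and not merely stopping product, which the text favours but does not spell out. The size is unknown: it depends on how many patients meet 3.4 within 28 days, how their scores differ, and whether that differs by arm. A reader might go further and conclude that the primary result will be biased; the documents do not show this, since losses that are alike in both arms cancel. The change is worth making because it is cheap and removes an avoidable source of doubt.

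The absence of the five classes from 3.3 is a minor cross-reference gap, for which neither bias nor size is claimed.

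**What to change.** 1. Reword 3.4, and the antibiotic sentence in 4.1, so that the listed events stop the study product but do not end follow-up.
2. In 4.1, schedule the t4 Chalder questionnaire 28 days after randomisation for every randomised patient who has not withdrawn consent, whether or not treatment was completed.
3. In 7.2, state that these scores are analysed in the assigned arm in the intention-to-treat analysis.
4. As a clarification, add to 3.3 regular ongoing use of any of the five classes barred by 4.1, and check it with one REDCap item before randomisation at Visit 2. This also catches drugs started in the run-in.

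The cost of items 1 to 3 is one extra questionnaire per withdrawn patient, and some t4 scores will be affected by the other drug. Item 4 costs one line and one screening item. It may slow recruitment slightly, and it makes explicit that the results do not cover patients already taking these drugs regularly, whom 4.1 bars in any case.
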